3. GENERAL DATA ANALYSIS CONSIDERATIONS

3.1 Analysis Set(s)

Primary and secondary analyses will be carried out among the following populations:

Screened Population: Includes all participants who were screened for potential enrollment.

Injection Population: Includes enrolled participants who receive at least one injection of CAB LA.

Safety Population: Includes enrolled participants who began step 1 (oral phase).

Enrolled Population: Includes all enrolled participants.

Seroconverter Population: Includes all enrolled participants who seroconverted during the study.

TDF/FTC Population: All enrolled participants who were provided TDF/FTC during the study.

3.2 Statistical Analysis Issues

AEs will be tabulated using MedDRA preferred terms. The number and percentage of participants experiencing each specific AE (All AEs, Grade 2 or higher, and SAEs) will be tabulated by severity and by relationship to study product. For the calculations in these tables, each participant's AEs will be counted once as the maximum severity and relationship to study product. AEs leading to temporarily or

permanently stopping drug will also be summarized. Methods for imputation of missing dates are described in Appendix C

4. INTERIM ANALYSIS AND DATA MONITORING COMMITTEE

See: Study progress, data, and safety data monitoring plan (SPDSMP) for a detailed description of the safety monitoring committee (SMC) report and data and safety monitoring board (DSMB) report for this study.

5. GENERAL ANALYSIS METHODS

[figure not shown]
Within the single arm, all primary and secondary outcome proportions with 95% CIs will be calculated.

6. TRIAL PARTICIPANT DISPOSITION

6.1 Disposition of Participants

The study will recruit participants to ensure that at least 50 participants progress to the injection phase, therefore more than 50 participants will be screened and enrolled.

Consort Diagram

¹Conditions in Step 1 that could disqualify a participant from transitioning to Step 2 are as follows:

- Pill count suggestive of less than 50% adherence at the Week 4 visit
- Missed or delayed Week 4 visit
- Grade 2 ALT at week 4, or grade 3 and above ALT anytime in step 1
- Grade 3 AE that is related to study product anytime in step 1, excluding ALT & CPK
- Grade 4 AE anytime in step 1, excluding ALT & CPK
- Grade 3 and above CPK and < Grade 3 ALT
- At substantial risk of HIV infection and/or qualifies for oral PrEP by local guidelines
- Any HIV reactive/positive test

Participant enrollment inclusion and exclusion criteria (see study protocol)

A. Inclusion Criteria

- 1) Assigned male at birth (including MSM, TGW, and gender non-conforming people)
- 2) At enrollment, below 18 years of age
- 3) At enrollment, body weight ≥ 35 kg (77 lbs.)
- 4) Willing to provide written informed assent/consent for the study and/or able to obtain written parental/guardian informed consent
- 5) Self-reported sexual activity with a male in the past 12 months
- 6) In general, good health, as evidenced by the following laboratory values:
 - a. Non-reactive / negative HIV test results
 - b. Absolute neutrophil count > 799 cells/mm³
 - c. Platelet count $\geq 100,000$ /mm³
 - d. Hemoglobin > 11 g/dL
 - e. Calculated creatinine clearance ≥ 60 mL/minute using the modified Schwartz equation (\leq grade 2)
 - f. Alanine aminotransferase (ALT) < 2.0 times the upper limit of normal (ULN) and total bilirubin (Tbili) $\leq 2.5 \times$ ULN
 - g. Hepatitis B virus (HBV) surface antigen (HBsAg) negative and accepts vaccination
 - h. HCV Antibody negative
- 7) Willing to undergo all required study procedures
- 8) If currently on PrEP from a non-study source, willing to stop said PrEP prior to enrollment and agree to switch to oral CAB for the lead-in period and CAB LA injections.

B. Exclusion Criteria

- 1) Co-enrollment in any other HIV interventional research study or other concurrent studies which may interfere with this study (as provided by self-report or other available documentation);
- 2) Past or current participation in HIV vaccine trial with exception for participants who can provide documentation of receipt of placebo;
- 3) Exclusively had sex with biological females in lifetime;
- 4) In the last 6 months (at the time of screening):
 - active or planned use of any substance use which would, in the opinion of the site investigator, would hinder study participation (including herbal remedies), as described in the IB or listed in the SSP, and/or Protocol Section 4.4
- 5) Known history of clinically significant cardiovascular disease, as defined by history/evidence of symptomatic arrhythmia, angina/ischemia, coronary artery bypass grafting (CABG) surgery or

percutaneous transluminal coronary angioplasty (PTCA) or any clinically significant cardiac disease;

- 6) Inflammatory skin conditions that compromise the safety of intramuscular (IM) injections;
- 7) Tattoo or other dermatological condition overlying the buttock region that may interfere with interpretation of injection site reactions;
- 8) Current or chronic history of liver disease (e.g., non-alcoholic or alcoholic steatohepatitis) or known hepatic or biliary abnormalities (with the exception of Gilbert's syndrome, asymptomatic gallstones, or cholecystectomy);
- 9) Known history of clinically significant bleeding;
- 10) Surgically-placed or injected buttock implants or fillers, per self-report. Contact the CMC for guidance regarding questions about individual cases
- 11) A history of seizure disorder, per self-report;
- 12) Medical, social or other condition that, in the opinion of the site investigator, would interfere with the conduct of the study or safety of the participant (e.g., provided by self-report, or found upon medical history and examination or in available medical records);
- 13) Plans to move out of the geographic area within the next 18 months or otherwise unable to participate in study visits, according to the site investigator.

6.2 Treatment Exposure

During step 1 (oral phase) staff are required to observe participants take one pill at enrollment, week 2 and week 4. Pill counts will occur at visits for week 2 and 4.

All injections during step 2 (injection phase) will be administered (and therefore directly observed) by study staff. Injections will be considered “on-time” if they occur in the visit window, described in the secondary analyses (section 12).

Blood samples will be collected throughout the study from all participants and assayed for plasma CAB concentrations. PK sample times include pre-dose trough samples at W5, W9, W17, W25, and W33 (final concentration in injection phase), 1-week post injection samples at W6, W10, W18, W26, W34, with a final sample at +8-weeks following the final injection. For participants advancing to Step 3 and do not elect to continue with CAB injections, additional follow-up samples will be collected at +24, +36 and +48-weeks following the final injection and at the HIV confirmatory visit.

6.3 Protocol Deviations

Protocol deviations will be summarized in regular reports to the SMC, the details of which are available in the SPDSMP. Serious protocol deviations may result in participants being terminated from the trial and/or being excluded from analyses. The decision to exclude participant data from the analyses will be made based on independent review. Deviations resulting in failure to progress to the injection phase would exclude such participants from the pertinent analysis datasets (except for the secondary safety analyses, which are limited to the oral phase only).

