### 7.5 Blinding

Participants and site staff will be unblinded throughout the trial.

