## **7.7 Primary Analyses**

All participants who receive at least one injection will contribute to the primary analyses. When the use of descriptive statistics to assess group characteristics or differences is required, the following methods will be used: for categorical variables, the number and percent in each category; for continuous variables, the mean, median, standard deviation, quartiles and range (minimum, maximum).

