### **7.7.1 Safety Endpoints**

The primary safety analysis will include Grade 2 or higher clinical and laboratory events that occur from the initial injection to 48 weeks after the last injection among participants who receive at least one injection.

To assess safety, the number and the percent of participants experiencing each safety endpoint will be tabulated. Each participant will contribute once in each category (for example, only for the highest severity AE for each participant) for the calculation of event rates. Exact binomial confidence intervals will be calculated for each safety endpoint.

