8.1 Safety endpoint analysis

Cohort: Injection population

Analysis description: Number and percent of participants experiencing any Grade 2 or higher clinical adverse events (AEs) or laboratory abnormalities (reported as adverse events) from the first injection visit to 8 weeks after the last Step 2 injection visit, or Week 41, whichever comes first. See Section 3.2 for details regarding aggregation and tabulation of AEs.

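### SAP 6.3 allows participants with serious protocol deviations to be excluded from analyses without exempting the primary analyses, which the protocol says include everyone injected

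*SAP*

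**What the plan says.** **Protocol.** Section 7.7 fixes the primary population without exception: "All participants who receive at least one injection will contribute to the primary analyses". Section 7.7.1 uses the same population for safety, counting events from "the initial injection to 48 weeks after the last injection among participants who receive at least one injection". Only the population matters here, not the length of the window.

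**SAP, analysis sets.** Section 3.1 defines the Injection population in the same way: "Includes enrolled participants who receive at least one injection of CAB LA". Section 8.1 applies it to the safety endpoint ("Cohort: Injection population") and 8.2 applies it to tolerability. For acceptability, 8.3.1 uses the Injection and Enrolled populations and 8.3.2 uses the Injection population. None of these sections mentions removal for a deviation.

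**SAP, deviations.** Section 6.3 states: "Serious protocol deviations may result in participants being terminated from the trial and/or being excluded from analyses". It continues: "The decision to exclude participant data from the analyses will be made based on independent review". A separate sentence covers people who never reach injection: "Deviations resulting in failure to progress to the injection phase would exclude such participants from the pertinent analysis datasets". The one exception in that sentence is for the oral-phase secondary safety analyses.

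**The concern.** If the clause in 6.3 were applied to an injected participant in a primary analysis, it would override the population that the protocol fixes and that the SAP itself defines. The SAP does not say which text prevails.

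The matter is sharpest for tolerability. SAP 8.2 counts as possible failures people who stop injections because they refuse further participation or product, do not comply with procedures, or cannot keep to the visit schedule. Protocol 3.6 and 5.16 allow the investigator, after consultation or agreement, to withdraw a participant for not complying with procedures. The same conduct could therefore be an endpoint event and also, if judged a serious deviation, a reason for exclusion. Excluding that person would remove a tolerability failure. It would also remove a non-completer from the completion endpoint in SAP 8.3.1.

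**Working it through.** **Does 6.3 reach injected participants?** Its first sentence is general. Participants who fail to reach injection have their own sentence, so the general rule is not confined to them. It is not confined to secondary or sensitivity analyses either.

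**Do the endpoint definitions already settle the matter?** SAP 8.3.1 gives special handling to confirmed HIV infection, death, early study closure and HBV infection when it defines completion. Deviation is not on that list. Under 8.3.1 alone, an injected participant withdrawn for non-compliance with injections outstanding would be a non-completer. Under 6.3 the same person could be left out.

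**The plan's own precision figure.** Protocol Table S1 and SAP Table 2 assume n = 50. The normal-approximation half-width is 1.96 × √(p(1−p)/50). For p = 0.1, 0.2, 0.3, 0.4 and 0.5 it gives 0.0832, 0.1109, 0.1270, 0.1358 and 0.1386. These match the printed values after rounding. SAP 6.4 says that enrolment stopped at nine.

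**Effect of one exclusion.** With x events among n participants:

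- dropping one participant with an event lowers the proportion by x/n − (x−1)/(n−1) = (n−x)/[n(n−1)];
- dropping one participant without an event raises it by x/(n−1) − x/n = x/[n(n−1)].

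The documents do not give the number injected; it can be anything from 0 to 9. The table assumes nine unless stated. All event counts are hypothetical. Intervals are exact binomial at 95%, the method that protocol 7.7.1 names for safety.

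| Case | All kept | One dropped | Change (points) |
|---|---|---|---|
| Only event dropped | 1/9 = 11.1% (0.3 to 48.2) | 0/8 = 0% (0 to 36.9) | −8/72 = −11.1 |
| One of two events dropped | 2/9 = 22.2% (2.8 to 60.0) | 1/8 = 12.5% (0.3 to 52.7) | −7/72 = −9.7 |
| Non-event dropped | 2/9 = 22.2% (2.8 to 60.0) | 2/8 = 25.0% (3.2 to 65.1) | +2/72 = +2.8 |
| Completion, non-completer dropped | 7/9 = 77.8% (40.0 to 97.2) | 7/8 = 87.5% (47.3 to 99.7) | +7/72 = +9.7 |
| Eight injected, only event dropped | 1/8 = 12.5% (0.3 to 52.7) | 0/7 = 0% (0 to 41.0) | −7/56 = −12.5 |
| Planned size, event dropped | 5/50 = 10.0% (3.3 to 21.8) | 4/49 = 8.2% (2.3 to 19.6) | −45/2450 = −1.8 |
| Planned size, non-event dropped | 5/50 = 10.0% (3.3 to 21.8) | 5/49 = 10.2% (3.4 to 22.2) | +5/2450 = +0.2 |

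At the planned size one exclusion changes little. At nine or fewer it can remove the only event.

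**The case against.** The clause is permissive and requires independent review. Other parts of the SAP point toward full inclusion. Section 2.2 announces an intention-to-treat analysis of the primary safety endpoint. Section 12.3 follows injected participants for about 36 weeks whether or not they had all five injections, and keeps early terminators with censoring. Section 12.2 reports safety in everyone who began the oral phase. The SAP plans to count non-compliance as a tolerability reason and nowhere names it as a serious deviation. Protocol 5.9 freely allows visits outside the target window, so a late visit need not be a deviation at all. Section 6.3 also refers to a separate monitoring plan for deviation reporting. That plan is not among the documents and might contain criteria.

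Most of this stands and limits the point. It does not remove it: 6.3 does not exempt sections 2.2, 8 or 12, and it cites the monitoring plan for reports to the monitoring committee, not for exclusion criteria.

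A reader might go further in three ways, none of which the documents support:

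- **That reviewers would know the outcomes.** The protocol says only that "Participants and site staff will be unblinded throughout the trial". What the independent reviewers see, and when, is not stated. Outcome-aware review is neither established nor ruled out.
- **That exclusions could not be checked.** The SAP plans a participant flow diagram, deviation summaries and listings of events of special interest, and the protocol plans a listing of expedited events. A reduced denominator would show in so small a study. What is missing is a requirement to list each excluded participant with the reason.
- **That exclusion always favours the product.** For safety, dropping someone without an event raises the rate, as the table shows. The favourable direction holds only where the excluded person is a tolerability failure or a non-completer.

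**Conclusion.** The conflict is in the text. SAP 6.3 permits a deviation-based exclusion that protocol 7.7 does not allow for injected participants and that the SAP's Injection population does not contain. The criteria, timing and blinding of the review are not stated.

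The practical risk is that conduct counted as a tolerability failure or non-completion could also serve as the reason for removing the participant. For the safety proportion the effect can go either way.

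If all nine were injected, one exclusion moves a primary proportion by up to about 11 points in the cases shown, and somewhat more if fewer were injected. The exact intervals are wide and overlap heavily, and the plan sets no test or threshold that such a shift would cross. The consequence is a distorted description, not a changed decision. Nothing in the documents shows that anyone was excluded.

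**What to change.** Add to SAP 6.3: *No participant with at least one injection will be removed from the primary safety, tolerability or acceptability analyses because of a protocol deviation. Any deviation-based exclusion will be confined to a labelled sensitivity analysis that lists each omitted participant and the reason.*

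The cost is two sentences in the SAP. No new data are needed, and the protocol and clinical procedures stay as they are. If the analyses have already been run, the report should say whether the clause was used and, if so, show the primary results with every injected participant included.

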6.4 Unplanned enrollment discontinuation

In January 2022 the HPTN leadership determined that the study accrual rate was insufficient to meet the target enrollment in a reasonable amount of time, and study enrollments were stopped after a total accrual of nine participants.

7. BASELINE DATA

The following data will be described overall, and by site:

Demographics (Table 1):

- Age (continuous – mean, SD, median, min max; categorical (≤ 16 , > 16): n (%))
- Gender identity
- Race
- BMI
 - Age standardized BMI z-score (continuous – mean, SD, median, min max)
 - Classification as obese, overweight, normal, thinness, severe thinness based on z-score
 - *Note: The Clinical Study Report will report BMI without the use of z-scores*
- Housing security*
 - Do you have a regular place or home where you stay and store your things? (yes/no)
- Food security*
 - In the past 6 months, how frequently did you worry that your household would not have enough food?

Sexual behaviors / HIV Risk Perception (Table 2):

During the past month the participant had*:

- a primary partner
- transactional sex with male sex partners
- # male and/or transgender female sex partners
- # male and/or transgender female sex partners who are reported to be HIV positive
- # episodes of receptive anal sex
- # episodes of receptive anal sex without condom
- # episodes of receptive anal sex without condom, with HIV+ or unknown partner
- # episodes of insertive anal sex
- # episodes of insertive anal sex without condom
- # episodes of insertive anal sex without condom, with HIV+ or unknown partner
- STIs present at enrollment:
 - Gonorrhea
 - Trachomatis
 - Syphilis
- Hepatitis testing at screening/enrollment
 - HBV
 - HCV

- HIV risk perception*:
 - How much do you personally feel at risk of getting infected with HIV?

Mental health (Table 3):

- Depression indices¹
 - CES-D-10* (continuous – mean, SD, median, min max; categorical (≤ 10 : not depressed, > 10 : depressed): n (%))
 - PHQ9 (continuous – mean, SD, median, min max; categorical (none-minimal, mild, moderate, moderately severe, severe): n (%))
- Intimate partner violence (IPV)*
 - In the past 6 months, have any of your partners punched, slapped, kicked, bit you, or caused you any type of physical harm?
 - In the past 6 months, have any of your partners insulted, ignored or humiliated you, yelled at you, or made you feel ashamed or bad about yourself?
 - In the past 6 months, have any of your partners forced you to have sex or perform any sexual act, or touched you sexually in any way that you did not want?
 - In the past 6 months, have any of your partners made you feel afraid, unsafe or in danger?
- Primary care post-traumatic stress disorder screening questionnaire (PC-PTSD-4)* (continuous – mean, SD, median, min max; categorical (≤ 2 : no PTSD, > 2 : potential PTSD): n (%))
 - *Note: The Clinical Study Report will not include this summary of PC-PTSD-4*
- alcohol/substance use*
 - How often do you have a drink containing alcohol?
 - How often do you have six or more drinks on one occasion?
 - In the past month, did you have a drink containing alcohol just before or during sex?
 - In the past month, how often have you used each of the following substances?
 - Cannabis (Also called marijuana, pot, grass, dakka, dagga or hash)
 - Amphetamine-type stimulants (For example Tik/Crystal Meth, ecstasy, speed, or diet pills)
 - Prescription drugs for non-prescription purposes (For example codeine (including cough syrup), efavirenz, valium)

¹Internal consistency of Depression Index summaries (*addendum to Table 3*):

1. Tabular cross-frequency of the categories for CES-D-10/PHQ9
2. Scatterplot of the values of either index, with color-coding based on whether they agree on qualitative risk of depression
 - a. *Note: The internal consistency evaluations will not be included in the Clinical Study Report*

*CASI questionnaire variables

8. PRIMARY ANALYSES

For each of the three primary endpoints the number and proportion of participants will be computed along with corresponding 95% confidence intervals. Each summary will be provided both overall and by site. Endpoint descriptions are available in section 2.2.

8.1 Safety endpoint analysis

Cohort: Injection population

Analysis description: Number and percent of participants experiencing any Grade 2 or higher clinical adverse events (AEs) or laboratory abnormalities (reported as adverse events) from the first injection visit to 8 weeks after the last Step 2 injection visit, or Week 41, whichever comes first. See Section 3.2 for details regarding aggregation and tabulation of AEs.

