### **2.2 Secondary Objectives**

- To examine adherence to and timeliness of injections over time among adolescent participants who are provided CAB LA and information regarding its safety and unknown efficacy.
- To examine patterns of sexual risk behavior over time among adolescent participants who are provided CAB LA and information regarding its safety and unknown efficacy.
- To evaluate the safety of CAB LA for 48 weeks of follow-up after final injection.
- To characterize the pharmacokinetics of CAB LA.

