### 7.8.2 Safety Endpoints

Secondary safety analyses will be summarized using the same method described in section 7.7.1, applied over the oral phase only (week 0 to week 4) and the aggregate oral+injectable+follow-up period.

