### 7.8.3 AEs and Serious Adverse Events (SAEs)

AEs and SAEs will be summarized using the same method described in section 7.7.3, applied over the oral phase only (week 0 to week 4) and the aggregate oral+injectable+follow-up period.

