2.2 Study Objectives and Endpoints

Primary objectives:

- To evaluate the safety, tolerability, and acceptability of CAB LA in healthy, HIV-uninfected male adolescents aged below 18 years.

Secondary objectives:

- To examine adherence to and timeliness of injections over time among adolescent participants provided CAB LA and information regarding its safety and efficacy.
- To examine patterns of sexual risk behavior over time among adolescent participants provided CAB LA and information regarding its safety and efficacy.
- To evaluate the safety of oral CAB during step 1 (oral phase) as well as all study products during the aggregate oral+injectable period for all enrolled participants. Additionally, we will include an intention to treat analysis for the primary safety endpoint.
- To characterize the pharmacokinetics of CAB LA
- Additional exploratory analyses will be done with the laboratory and clinical data, including resistance mutations

To achieve the primary and secondary objective, the planned primary and secondary endpoints are:

Primary endpoints:

Safety endpoint: Proportion of participants experiencing any Grade 2 or higher clinical adverse events (AEs) and laboratory abnormalities among participants who receive at least one injection of CAB LA. Laboratory abnormalities include grade 2 or above on tests include (CRF: Chemistry Panel, Fasting Lipid Test Results, Urinalysis, Hematology):

- Renal function: Creatinine, Creatinine clearance
- Hematology: Hemoglobin, Platelets, WBC, Neutrophils, Lymphocytes
- Liver function: Alkaline phosphatase, AST, ALT, Total bilirubin
- Electrolytes: Phosphorus, Calcium
- Other chemistries: CPK, Glucose, Amylase, Lipase,
- Urine test: Protein, Glucose
- Fasting Lipid Test Results: Total cholesterol, Triglycerides, LDL, HDL

Tolerability endpoint: Proportion of participants who receive at least 1 injection and who discontinue receiving injections prior to the full course of injections due to intolerance of injection, frequency of injections or burden of study procedures. Reasons for intolerance may include:

- Injection site reaction
- Participant refused further participation¹
- Participant lost to follow-up
- Participant is unwilling or unable to comply with required study procedures
- Participant refused further study product use
- Participant unable to adhere to visit schedule

¹Excluding cases in which reason for termination is unrelated to intolerance

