Acceptability endpoints: Proportion of participants who complete all scheduled injections and proportion of participants who receive at least one injection who would consider using CAB LA for HIV prevention in the future. This endpoint will be evaluated using CASI questionnaires at the last injection visit (Step 2, week 33) for participants who do not have acceptability data at the Step 2, week 33 visit (either due to a change in when the questionnaire items were administered², missed the final injection visit, or discontinue injections early) and continue to step 3, acceptability endpoints are evaluated during the follow up phase (step 3, week +12). The primary acceptability outcome is:

If you wanted to protect yourself from getting HIV, which of the following product(s) would you prefer to use?

- Prefer not using a product
- Condoms only
- Oral PrEP pills only
- Injectable PrEP only
- Condoms and oral PrEP pills together
- Condoms and injectable PrEP together
- Prefer not to answer

Secondary endpoints:

- Proportion of injection visits that occurred “on-time”
 - The target visit window for the week 5 injection is 0-3 days after the Week 5 visit date (allowing for the injection occurring on a different day from the W5 visit) and is +/-3 days from the target injection date for all other injection visits. Visits happening within the target window are considered “on-time”
- Change from enrollment of self-reported sexual behavior (number of sexual partners, increased episodes of anal sex without a condom) during the study period
- Proportion of participants experiencing Grade 2 or higher clinical AEs and laboratory abnormalities in the oral phase and the aggregate over the entire study period
- Plasma CAB pharmacokinetics

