12.1 Plasma CAB pharmacokinetics

Analysis details are provided in the current version of the Pharmacokinetics Analysis Plan

12.2 Proportion of participants experiencing Grade 2 or higher clinical AEs and laboratory abnormalities in the oral phase and over the entire study period

Cohort: Safety population

Analysis description: Number and percent of participants experiencing any Grade 2 or higher clinical adverse events (AEs) or laboratory abnormalities from:

1. enrollment to week 5 (oral phase (step 1), including interim visits).
2. enrollment to 8 weeks following the last injection received (aggregate over oral+injection phases (step 1-step 2) including interim visits)

12.3 Proportion of participants receiving one or more injections who experience Grade 2 or higher clinical AEs and laboratory abnormalities from initial injection to 36 weeks later

Population: Injection population

Analysis description: Number and percent of participants experiencing any Grade 2 or higher clinical adverse events (AEs) or laboratory abnormalities from the first injection visit to approximately 36 weeks later regardless of whether participants received all 5 injections. For participants receiving all 5 injections, the end date is 8 weeks following the week 33 injection visit. For participants discontinuing study product early and moving on to Step 3, the end date is 36 weeks after the initial injection. Participants who terminate early are included in the analysis and censored at the date of termination.

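### The primary Grade 2+ safety window is 48 weeks after the last injection in the protocol and 8 weeks in the SAP, and no SAP analysis covers the 48-week post-injection objective

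*SAP*

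**What the plan says.** **Primary safety window.** Protocol 7.7.1 includes "events that occur from the initial injection to 48 weeks after the last injection among participants who receive at least one injection". SAP 8.1 counts events "from the first injection visit to 8 weeks after the last Step 2 injection visit, or Week 41, whichever comes first". Both use participants with at least one injection and the same grade threshold. The endpoint definitions (Protocol 7.2.1, SAP 2.2) give no time limit.

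**Safety after the final injection.** Protocol 2.2 lists a secondary objective: "To evaluate the safety of CAB LA for 48 weeks of follow-up after final injection". Protocol 7.8.2 has the safety analysis "applied over the oral phase only (week 0 to week 4) and the aggregate oral+injectable+follow-up period", and 7.8.3 does the same for AEs and SAEs: "described in section 7.7.3, applied over the oral phase only (week 0 to week 4) and the aggregate oral+injectable+follow-up period".

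The SAP objective in 2.2 covers oral CAB in Step 1 "as well as all study products during the aggregate oral+injectable period for all enrolled participants", with no follow-up period. Yet the secondary endpoint in SAP 2.2 is still worded "in the oral phase and the aggregate over the entire study period", and the heading of SAP 12.2 still promises "laboratory abnormalities in the oral phase and over the entire study period". Item 2 of SAP 12.2 then ends 8 weeks after the last injection received and is labelled as Steps 1 and 2.

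**Data collection.** Protocol 6.1 collects AEs from enrolment until follow-up ends. SAP 2.1 keeps the 48 weeks of follow-up after the last injection.

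**The concern.** The primary result is a cumulative proportion of participants with any Grade 2+ event. It can only rise as the window lengthens, so the window is part of the endpoint's definition. With two windows in force, the headline percentage could be computed either way and each would follow a current document.

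The omitted period matters by the protocol's own account. Section 1.10 says CAB stays detectable for a year or more after an injection, and Section 1.5.2 gives a median time to undetectable drug of 42.7 weeks in men. An 8-week window covers little of that tail.

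The SAP change history says primary and secondary outcomes and analyses were updated. Its reasons are the Step 3 CAB LA option and harmonization with another SAP. It names neither the shorter window nor the loss of the 48-week objective. The trial is open label, enrolment stopped in January 2022 and SAP version 2.0 was signed in January 2023, so an undeclared difference in a primary window invites questions.

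**Working it through.** **Inputs.** Step 2 injections at Weeks 5, 9, 17, 25 and 33 (Protocol 4.1). Windows from Protocol 7.7.1 and SAP 8.1. Visit schedules from Protocol Appendices II, III and IV. Total accrual of nine from SAP 6.4.

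**1. The SAP's own figure.** 33 + 8 = Week 41, the cap in SAP 8.1. 41 − 5 = 36 weeks, the length given in SAP 12.3. Both reproduce.

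**2. Window lengths, anchored on the last Step 2 injection.** Protocol length = (last + 48) − 5. SAP 8.1 length = (last + 8) − 5.

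| Injections received | Last at week | Protocol 7.7.1 (weeks) | SAP 8.1 (weeks) | Left out |
|---|---|---|---|---|
| 1 | 5 | 48 | 8 | 40/48 = 83% |
| 2 | 9 | 52 | 12 | 40/52 = 77% |
| 3 | 17 | 60 | 20 | 40/60 = 67% |
| 4 | 25 | 68 | 28 | 40/68 = 59% |
| 5 | 33 | 76 | 36 | 40/76 = 53% |

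The cap can shorten the SAP window further. If the fifth injection is 2 weeks late, only 41 − 35 = 6 weeks after it are counted.

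**3. Which last injection.** Protocol 7.7.1 does not say Step 2. For a participant who continues CAB LA, the literal end is 33 + 40 + 48 = Week 121 (last dose at +40) or 33 + 48 + 48 = Week 129 (last dose at +48). Both lie past nominal exit at 33 + 48 = Week 81. Cut off at exit, the gap is still 81 − 41 = 40 weeks.

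**4. Scheduled observation.** Calendar weeks overstate what is lost, because Step 3 tests less. After five injections there are 10 Step 2 visits, each with examination, CBC, chemistry, liver tests and urinalysis; lipids are at Week 34 only. The +8 visit is counted inside the SAP window, and early-discontinuation visits are not counted. Assessments after the SAP 8.1 window:

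| Assessment | Oral PrEP | CAB LA |
|---|---|---|
| History and examination | 4 of 14 (29%) | 5 of 15 (33%) |
| Liver tests | 4 of 14 (29%) | 2 of 13 (15%) |
| CBC | 2 of 12 (17%) | 2 of 12 (17%) |
| Full chemistry | 0 of 10 (creatinine only, 4 visits) | 2 of 13 (15%) |
| Urinalysis | 2 of 12 (17%) | 0 of 10 |
| Fasting lipids | 0 of 1 | 0 of 1 |

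After one injection followed by oral PrEP there are only 2 Step 2 visits. Then 4 of 6 examinations and liver tests (67%) and 2 of 4 CBCs (50%) fall after the window.

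**5. Where a 48-week analysis might sit in the SAP.**
- 12.2 item 2 ends 8 weeks after the last injection and is labelled Steps 1–2.
- 12.3 ends at Week 5 + 36 = Week 41. That is 36 weeks after the last injection for a one-injection participant and 8 weeks for a completer. It never reaches 48.
- The listings of AEs of special interest in Appendix A cover Steps 1 and 2.
- Section 9 refers back to 8.1 and to the closed DSMB report.
- Section 3.2 tabulates AEs with no window.
- Section 9.2 summarises laboratory values only, with no stated end.
- 12.6 is the only analysis that explicitly uses Step 3 data, and it concerns drug resistance.

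**6. Effect on the estimate.** With at most nine participants, one more with an event adds at least 1/9 = 11.1 percentage points. For illustration only, assume a constant event rate, which the documents do not give. A proportion p at 36 weeks then becomes 1 − (1 − p)^(76/36) at 76 weeks: 0.10 becomes 0.20, 0.30 becomes 0.53 and 0.50 becomes 0.77. Thinner laboratory testing in Step 3 would make the real increase smaller.

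**The case against.** The strongest reply is that SAP 12.3 reduces the loss. SAP 2.2 promises an intention-to-treat analysis of the primary safety endpoint, and 12.3 follows early discontinuers for 36 weeks from first injection, into Step 3. Counting it, the protocol-window weeks with no Grade 2+ proportion fall to 12 of 48 (25%), 16 of 52 (31%), 24 of 60 (40%) and 32 of 68 (47%) for one to four injections. After one injection then oral PrEP, only the +48 visit is missed: 1 of 6 examinations and liver tests, and 1 of 4 CBCs. This is correct, and it means the 83% to 59% figures for early stoppers describe SAP 8.1 alone. It does not settle the primary window, it adds nothing for completers (40 of 76 weeks, 53%), and it leaves the 48-week objective unanswered.

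Second, SAP 3.2 and 9.2 do not exclude Step 3, and the last injection received in 12.2 could be read to include Step 3 doses. These are ambiguities, not analyses. The Steps 1–2 label points against that reading of 12.2, which in any case would never cover 48 weeks after a final injection.

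Third, the shorter window may be deliberate, since Step 3 mixes products and the analysis is descriptive with no test. That is a fair reason to prefer 8 weeks, but neither document states it, and Protocol 7.7.1 still says 48.

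Fourth, continuers dosed at +40 or +48 have only 8 or 0 weeks left before exit. This stands: the 48-week objective can be met only for participants who stop CAB LA early enough.

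**Conclusion.** The concern holds. The protocol and SAP define different windows for the same primary safety proportion, 40 weeks apart when anchored on the last Step 2 injection, and nothing else in the two documents settles which applies. The 48-week post-injection objective and the aggregates in Protocol 7.8.2 and 7.8.3 have no defined analysis in the SAP text.

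For completers, between 0% and 33% of scheduled assessments, depending on type and Step 3 product, fall after the SAP window. The primary proportion would change only if a participant's first Grade 2+ event since the first injection falls after that window; the documents give no basis for saying how likely that is. The calculation assumes nominal visit weeks. The conclusion on the missing analysis is limited to the SAP itself, since the monitoring plan it cites is a separate document not available here. This should be resolved before the primary safety result is reported.

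**What to change.** 1. Make Protocol 7.7.1 and SAP 8.1 agree. State one primary window, anchored on the last Step 2 injection, with the reason, and report the other as a named secondary analysis. Keeping 8 weeks as primary is acceptable if 7.7.1 is amended and the reason given, for example that Step 3 mixes products and reduces laboratory testing.
2. In either case, add a Step 3 summary or listing of Grade 2+ clinical and laboratory events from the end of the Step 2 window to study exit. Split it by product in use at onset (CAB LA or TDF/FTC), and report the period after the final injection for those who stopped CAB LA.
3. Bring SAP 12.2 item 2 into line with its heading and with Protocol 7.8.2 and 7.8.3.
4. State beside these results that Step 3 laboratory ascertainment is reduced: creatinine-only chemistry on oral PrEP, no fasting lipids, no scheduled urinalysis for CAB LA continuers and fewer CBCs. Step 3 rates are therefore not directly comparable with Step 2.
5. Record the decision in the SAP change history.

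The cost is wording and one table or listing for at most nine participants, from data already collected. The headline percentage may be higher under the longer window, which is why the product split and the ascertainment note are needed.
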